#### 6.1.2 Participant Screening Schedule

Potential participants for the study will be evaluated using a two visit screening method that will allow investigators to evaluate the participant's ability to provide a reproducible (15%) (*primary endpoint*) test scores to be enrolled. The entry procedures will be conducted according to the schedule in **Table 3**. After potential participants have completed the screening visits and the site has verified they meet all study inclusion criteria the participant will be randomized into the study.

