## 1.2 Study Purpose

This is a proof-of-concept phase 1/2a pilot and endpoint development study that is designed to provide initial evidence of biological activity of (-)-epicatechin. Primary endpoints include initial assessment of tissue-specific evidence of efficacy from muscle biopsy samples. Secondary endpoints include measures of strength and physical function, and safety and adverse event data. Pilot endpoints include assessment of mRNA and miRNA peripheral blood profiles and validation of non-invasive near-infrared spectroscopy (NIRS) muscle perfusion studies during exercise and a recumbent cycle exercise test that may be employed as endpoints in future clinical trials.

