*Hypothesis:* Changes in grip strength ( $\geq 5\%$ ), elbow flexion/extension isometric strength ( $\geq 5\%$ ), knee extension isometric muscle strength ( $\geq 1$  pound = 4.448 Newtons), pulmonary function derived maximal static airway pressures (MIP and MEP  $\geq 10$  cm H2O), and regional lean tissue mass by DEXA ( $\geq 2\%$ ) will be clinically significant and correlate with biomarker evidence for muscle regeneration and histological improvement in sarcomere morphology.

*Hypothesis:* Pilot data from exercise performance and strength evaluations in adults with Becker muscular dystrophy will determine the magnitude of response over time that will enable accurate power calculations for future clinical trials.

**Aim 3 (Safety Secondary Endpoints): Evaluation of safety and pharmacokinetic profiles of (-)-epicatechin in adults with Becker muscular dystrophy.** Assessments of safety will include a standard clinical safety panel including hematologic, hepatologic, renal and metabolic profiles. Pharmacokinetic studies will include repeat assessments of trough, 2 hour-post (peak) and 4-hour post dose (-)-epicatechin levels.

*Hypothesis (safety):* (-)-epicatechin given at 100mg/d orally will display an acceptable safety profile in BMD patients.

*Hypothesis (pharmacokinetics):* (-)-epicatechin given at 100mg/d orally in BMD patients will produce pharmacokinetic profiles similar to those seen in previously described studies in the literature.

**Aim 4 (Pilot Biomarker Endpoints): Pilot evaluation of disease- and epicatechin-specific circulating mRNA and miRNA blood profiles as pilot biomarkers for monitoring treatment efficacy.** Epicatechin stimulates follistatin expression in tissue and blood. In addition to its effects on muscle regeneration, follistatin is known to exert anti-inflammatory and anti-fibrotic effects via antagonism of activin and myostatin.

*Hypothesis:* Using gene array assays directed toward fibrosis- and inflammatory-oriented pathways, we expect treatment with (-)-epicatechin to induce detectable pre-/post-treatment differences in mRNA and miRNA expression that may be utilized as biomarkers of treatment effect for future clinical trials.

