## 6 RESEARCH DESIGN AND METHODS

### 6.1 Selection and Withdrawal of Participants

#### 6.1.1 Criteria for Enrollment

Ten participants will be studied in this initial pilot project.

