**Table 3: Study procedures**

Event	Screening  (Week -2 to Day 1)	Baseline (Day 1)	Week 1	Week 2	Week 4	Week 8	Early with- drawal
Informed consent	X						
Medical history	X	X		X	X	X	X
Vital signs	X	X		X	X	X	X
Physical examination	X	X		X	X	X	X
Blood & urine collection (safety, efficacy, PK )	X	X		X	X	X	X
ECG	X	X		X	X	X	
Other medications and dietary supplements	X	X			X	X	X
Adverse events		X		X	X	X	X
Functional assessments strength, 6MWT, recumbent graded exercise test, NIRS, PFTs		X			X	X	X
Blood tests: baseline and efficacy		X			X	X	X
Muscle Biopsy Tests: baseline and efficacy		X				X	
Dispense Epicatechin		X		X			

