## **11 STATISTICS**

Presented herein is the overall analysis plan. The main criterion for success of the study will be presence of one or more biologic or strength and performance outcome measures (Aims 1 and 2) that yield a response magnitude that allows for sufficient power in a Phase II B study with a sample size of 30 individuals. Analysis, employing both statistical and graphical presentations of data, will generally proceed from descriptions and simple comparisons to multiple variable models. This will help to ensure proper understanding of the data at each level before proceeding to the next. Descriptive analysis of means and proportions will characterize study participants overall as well as evaluate assumptions of normality and homoscedasticity. Any significant departures from these assumptions especially for the measurement variables will lead to normalizing or variance stabilizing transformations or, in the unlikely event these are not successful, to conversion to ranks. Baseline and screening measures will be used to calculate test-retest reliability using the intraclass correlation coefficient. Level of statistical significance is set at  $<0.05$ . Simple comparative analyses involving chi squares ttests and correlations will be used to assess and understand simple relationships, including defining first order interactions. Where possible we will perform longitudinal analyses using mixed models (using xtreg or xtmixed in STATA 12) to evaluate raw scale and percent change over time in study outcomes measures. These procedures will allow us to account for fixed and random effects as well as correlation between observations when we introduce repeated measures on the same individuals. If feasible with the small number of participants in the study and because there is little available data for individuals with Becker muscular dystrophy, this pilot data will be used to determine estimates of minimally important clinical difference (MCID) for each measure (defined as  $1/3$  S.D. for the population). Safety data will be compiled as tables of frequency and severity of adverse events by body system.

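### The 15% reproducibility rule for entry would bias the test-retest ICC upward for whichever measure it covers, because men who fail the rule are left out of the estimate

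*Combined protocol and SAP*

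**What the plan says.** Section 6.1.2 has candidates "evaluated using a two visit screening method", which judges each man's "ability to provide a reproducible (15" per cent) score. The full condition reads "ability to provide a reproducible (15%) (*primary endpoint*) test scores to be enrolled". The bracketed words stand where a test should be named. The 15% is not defined: it could be a difference relative to the mean of two scores, a difference relative to the first score, or something else. The inclusion and exclusion lists in section 6.1.1 do not contain the rule.

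Section 11 states: "Baseline and screening measures will be used to calculate test-retest reliability using the intraclass correlation coefficient". It does not give the form of the ICC. It says nothing about candidates who fail screening, about selection, or about a confidence interval for the ICC. The sample is small: "Ten participants will be studied in this initial pilot project" (section 6.1.1).

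In Table 3 the row "Functional assessments strength, 6MWT, recumbent graded exercise test, NIRS, PFTs" is marked at baseline, week 4, week 8 and early withdrawal, but not at screening.

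On purpose, section 1.2 describes the study partly as endpoint development. Aim 2 in section 1.4 says that the pilot exercise and strength data "will determine the magnitude of response over time that will enable accurate power calculations for future clinical trials".

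**The concern.** A test-retest ICC compares the spread between men with the disagreement between a man's two scores. If men whose two scores disagree by more than 15% are not enrolled, and the ICC is then calculated in the enrolled men, the large disagreements have been removed by rule before they are measured. The resulting ICC and within-man SD describe the test as seen through the filter, not the test itself.

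This matters because the study is meant to learn which measures are usable later. A filter of this kind can make a noisy test look about as reliable as a precise one.

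**Working it through.** The plan states no ICC, SD or power figure, so there is nothing of its own to reproduce. The check asks how far the rule would move an ICC.

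**Inputs from the documents:** a 15% tolerance and two screening visits (section 6.1.2); an ICC from screening and baseline measures (section 11); 10 men (section 6.1.1).

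**Assumed, because the documents do not give them:** between-man CV (CVb) 20-40%; within-man CV (CVw) mainly 5-20%; log-normal scores; rule taken as |x1 - x2| / mean ≤ 0.15; one-way ICC.

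**Formulas, with CVb = 20% and CVw = 10%**

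1. Proportion passing = 2Φ(0.15 / (√2 × CVw)) - 1. Here 0.15 / (1.414 × 0.10) = 1.061, which gives 0.711.
2. ICC without the filter = CVb² / [CVb² + (1 + CVb²) × CVw²] = 0.04 / (0.04 + 0.0104) = 0.794.
3. ICC in passers on the same pair. The rule cuts the difference between the scores and leaves their mean almost untouched. In a simulation of 2,000,000 men the apparent CVw in passers was 5.7%, so the error variance falls to (5.7/10)² = 0.325 of its true value. Between-man mean square = 2 × 0.04 + 0.0104 = 0.0904. Within-man mean square = 0.325 × 0.0104 = 0.0034. ICC = (0.0904 - 0.0034) / (0.0904 + 0.0034) = 0.928.

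**Simulated results, 2,000,000 men per setting**

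| CVb | CVw | Pass | ICC, all men | ICC, passers, rule's own pair | ICC, passers, second score with a fresh score |
|---|---|---|---|---|---|
| 20% | 5% | 97% | 0.939 | 0.950 | 0.942 |
| 20% | 10% | 71% | 0.794 | 0.928 | 0.822 |
| 20% | 15% | 52% | 0.631 | 0.931 | 0.685 |
| 30% | 5% | 97% | 0.971 | 0.976 | 0.972 |
| 30% | 10% | 71% | 0.892 | 0.964 | 0.909 |
| 30% | 15% | 52% | 0.786 | 0.963 | 0.823 |
| 40% | 5% | 97% | 0.982 | 0.985 | 0.983 |
| 40% | 10% | 71% | 0.933 | 0.978 | 0.943 |
| 40% | 15% | 52% | 0.860 | 0.976 | 0.886 |

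At CVw 20%, 41% pass, and true ICCs of 0.49-0.78 read 0.94-0.98 on the rule's own pair. The apparent CVw in passers never exceeds about 6%, so within any one CVb the own-pair ICC hardly changes as the test gets noisier. Dividing by the first score instead of the mean changes the own-pair ICC by 0.002 or less.

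**If men differ in their own variability.** With half at CVw 5%, half at 20%, and CVb 30%, the ICC is 0.793 in all men, 0.972 in passers on the rule's own pair, and 0.882 with a fresh second score. A fresh score then removes only part of the bias, because the filter keeps the steadier men.

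**Precision at n = 10.** An observed ICC of 0.90 gives F = 1.90 / 0.10 = 19 and a 95% interval of about 0.67 to 0.97 (one-way F method).

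**The case against.** The strongest reply is that the rule may not be in force. Its measure is an unfilled placeholder, it is missing from the entry criteria, and section 1.3 enrols on the inclusion criteria. The same paragraph of section 6.1.2 ends by saying that men are randomised, which section 6.1.3 contradicts, and section 6.2.1 has a placeholder of its own. This could be leftover template text. Table 3 also schedules no functional test at screening, so on that schedule the functional pair needed for both the rule and the ICC does not exist. Section 10.7.4 points the other way, since it has strength testing at each visit.

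Next, section 6.1.2 can be read as applying the rule to two screening scores, with the ICC bringing in a later baseline score. That is the milder column of the table. Finally, with 10 men the sampling error of the ICC can be as large as the bias.

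Much of this stands. It makes the bias conditional and its size unknown. It does not remove the point. Both the rule and the ICC are in the text, and nothing says that screen failures are included. Adding a screening test to Table 3, the obvious repair, could bring the bias into effect. A confidence interval shows imprecision but does not reveal or correct a systematic upward shift.

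**Conclusion.** The point holds in conditional form. For whichever measure the 15% rule covers, an ICC in enrolled men is biased upward and the within-man error downward. The bias is large when the ICC uses the rule's own pair and the test's CVw is not small against 15%: at CVw 10% and CVb 20-40%, 0.79-0.93 reads 0.93-0.98. It is about 0.01 or less at CVw 5% or below. With a fresh baseline score it is small at CVs of 20% and 10% (0.82 against 0.79), unless men differ much in their own variability. All of these sizes rest on assumed CVs.

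A reader might infer more than the documents support:

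- **That every ICC in the study is inflated.** Measures outside the rule are affected only if their errors correlate with those of the filtered test.
- **That a later trial would be undersized.** No section says that the ICC sets a sample size. Section 11 ties success to response magnitude, and the later trial's entry rules are unknown. If it kept the same filter, the conditional ICC would be the relevant one.
- **That the rule cannot apply to the primary endpoint because that is biopsy tissue, sampled once before treatment.** Section 1.2 does say "Primary endpoints include initial assessment of tissue-specific evidence of efficacy from muscle biopsy samples", but Aim 1 also covers blood markers such as plasma follistatin, and Table 3 marks a blood collection at both screening and baseline.
- **That 15% is too loose beside the 5-10% change in Aim 2.** One is a tolerance for a single man's repeat test and the other is a pre/post difference. The comparison has no bearing on the ICC.

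**What to change.** 1. **Section 11:** calculate the ICC and within-man SD from all candidates who completed both pre-treatment tests, including those who fail the 15% rule. If only enrolled men are used, report the ICC as conditional on passing, with the number screened out and a confidence interval, and do not use it to plan a trial without that filter.
2. **Section 6.1.2:** replace the placeholder with the named test and define the 15% metric.
3. **Sections 6.1.1, 6.1.2 and 11 and Table 3:** reconcile them on which test is repeated, at which visits, and whether the result decides entry.

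The text changes are short. Scores of screen failures must be retained, and the reported ICC may look less favourable. If the repeated test is a functional one, Table 3 must also show it at screening, which is an added assessment on the schedule as it stands.

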**Table 3: Study procedures**

Event	Screening  (Week -2 to Day 1)	Baseline (Day 1)	Week 1	Week 2	Week 4	Week 8	Early with- drawal
Informed consent	X						
Medical history	X	X		X	X	X	X
Vital signs	X	X		X	X	X	X
Physical examination	X	X		X	X	X	X
Blood & urine collection (safety, efficacy, PK )	X	X		X	X	X	X
ECG	X	X		X	X	X	
Other medications and dietary supplements	X	X			X	X	X
Adverse events		X		X	X	X	X
Functional assessments strength, 6MWT, recumbent graded exercise test, NIRS, PFTs		X			X	X	X
Blood tests: baseline and efficacy		X			X	X	X
Muscle Biopsy Tests: baseline and efficacy		X				X	
Dispense Epicatechin		X		X			

### 6.1.3 Randomization

This is an open-label pilot study, and will not utilize randomization in the study design.

## 6.2 Withdrawal of Participants

Participants are free to withdraw from the study at any time. Study investigators may elect to withdraw a participant from the study for reasons including an adverse event and inability to comply with study procedures. Reasons for withdrawal of all participants will be recorded for review by the Study Medical Monitor.

### 6.2.1 Follow-Up of Withdrawn Participants

Those participants who are withdrawn from study medication, but are still willing to finish study participation per protocol, will be followed with (*method*) testing for the remainder of the 8-week study period (8 months from participant's baseline visit). If participant agrees to follow-up, adverse event and medical event follow-up, along with basic safety data, will also be collected at scheduled study visits or via phone every 2 weeks for the remainder of the study period (through week 8).

## 6.3 Treatment of Participants

### 6.3.1 Epicatechin Administration

Participants will receive epicatechin by mouth 50mg twice per day (100mg per day total dose). Study medication will be supplied as a clear 25mg (#3) gelatin capsule without any inert fillers. Participants will take two capsules in the morning at approximately 7:30AM at least 15 minutes before the morning meal and two with the evening at approximately 7:30PM at least 1 hour after the evening meal as absorption is limited by some milk products.

For details on participant enrollment and randomization, please refer to the study procedures chart (Table 3) and pharmacy sections. When medications have been received, they should be dispensed to participants from their assigned investigational drug supply along with the medication instructions handout for parents and physicians.

### 6.3.2 Criteria for Dose Reductions

Dose reductions will occur due to adverse drug events and participants will not have their doses re-escalated during the course of the study. Criteria for dose reduction will include:

- Peak (-)-epicatechin PK level >4umol/ml
- Recurrent non-manageable headache
- Increase in baseline safety evaluations >1.5 ULN or 100% change from baseline, excepting CK, AST, ALT
- Abnormal coagulation studies (PT/PTT)
- Other Grade 4 adverse event

If participants require a dose reduction based on the criteria listed above follow the guidelines in Table 4 when reducing a participant's study medication dose.

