#### 3.1 Pharmacokinetics / Pharmacodynamics

(-)-Epicatechin is orally bioavailable, as the consumption of (-)-epicatechin or cocoa products can result in pharmacologically relevant levels of (-)-epicatechin and its metabolites in blood. In addition to the literature reviewed below, the results of a recent human pharmacokinetic study are presented in Section 6.3. The absorption of flavonoids occurs mainly in the small intestine and takes place within minutes. In the small intestine, flavanols are extensively glucuronidated and partially methylated [41, 42], allowing negligible amounts of native (-)-epicatechin in the mesenteric circulation.

[figure not shown]
In the liver, further glucuronidation, methylation, and sulfation can take place [41, 43, 44]. Several studies have determined the presence of these conjugates in the plasma and urine of rodents and humans [15, 19, 44-47], as well as in rat bile [43] and brain [48]. In plasma, (-)-epicatechin is present almost exclusively as conjugated metabolites [19, 47].

Total plasma concentrations of (-)-epicatechin plus its metabolites are found in the low-micromolar range as soon as 1 h after the consumption of a flavanol-rich food (cocoa), with  $T_{max}$  ~2 hours [11, 18-21, 45, 47-50]. The most abundant (-)-epicatechin metabolites detected in plasma after dark chocolate ingestion were (-)-epicatechin-3'- $\beta$ -D-glucuronide, (-)-epicatechin-3'-sulfate, and 3'-O-methyl(-)-epicatechin-5-sulfate [47]. A schematic representation of these metabolites is shown in Figure 2. In addition, significant levels of 3'-O-methyl(-)-epicatechin sulfates substituted in the 4' and 7 positions were identified [47].

Relative amounts of (-)-epicatechin metabolites identified in plasma in two separate studies are shown in Figure 3.

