**Figure 3: (-)-Epicatechin metabolite profile in plasma**

**A.** (-)-Epicatechin metabolite profile in plasma 2 hours after ingestion of 1.8 mg/kg body weight (-)-epicatechin [19]. Unmodified (-)-epicatechin represented <0.5%. **B.** Profile of (-)-epicatechin metabolites in plasma after ingestion of 100g of dark chocolate (79 mg (-)-epicatechin) [47]. Data are expressed as the percentage of total plasma AUC0-24 h. Unmodified (-)-epicatechin not detected. EC-3'-Gluc, (-)-epicatechin-3'-β-D-glucuronide; EC-4'-Gluc, (-)-epicatechin-4'-β-D-glucuronide; EC-7-Gluc, (-)-epicatechin-7-β-D-glucuronide; EC-3'-S, (-)-epicatechin-3'-sulfate; 3'Me-EC-5-S, 3'-O-methyl(-)-epicatechin 5-sulfate; 3'Me-EC-4'-S, 3'-O-methyl(-)-epicatechin 4'-sulfate; 3'Me-EC-7-S, 3'-O-methyl(-)-epicatechin 7-sulfate; and 4'Me-EC-5-S, 4'-O-methyl(-)-epicatechin 5-sulfate.

The  $T_{max}$  (time to maximum plasma concentration) of (-)-epicatechin and most of its metabolites is 1-2 hours, elimination half-time ( $t_{1/2}$ ) from plasma is ~2-2.5 hours, and over 90% of the urinary excretion of these compounds was complete by 8 hours [17, 19, 21].

Oral bioavailability (peak plasma concentration/mg ingested) for (-)-epicatechin in cocoa/chocolate is ~10-20 nM/mg ingested (Table 2). Assuming ~3L plasma in a 75 kg man [51], oral bioavailability of (-)-epicatechin (% ingested dose in plasma at  $C_{max}$ , total epicatechin and metabolites), can be estimated as 1-2%. A value of 1.1% was reported for a 45 mg (-)-epicatechin dose in a green tea catechin mixture [17].

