**Table 2: Selected human oral bioavailability studies of (-)-epicatechin**

Reference	Test Article	(-)-Epicatechin (mg)	Peak (-)-Epicatechin Species in Plasma (nM)	Peak (-)-Epicatechin Exposure (nM/mg)
Loke, W.M., et al., 2008 [52]	(-)-Epicatechin	200	3570	17.85
Ottaviani, J.I., et al., 2011 [18]	(-)-epicatechin added to cocoa vehicle	125 (mean)	~900	~7.2
Ottaviani, J.I., et al., 2012 [19]	Cocoa drink	135 (mean)	1245	9.3
Actis-Goretta, L., et al., 2012 [47]	Dark Chocolate	79	873	11.1
Donovan, J.L., et al., 2006 [53]	Cocoa drink	55	630	11.5
Schroeter, H., et al., 2006 [11]	Cocoa flavanols: 917 mg	174	~1950	~11.2
Baba, S., et al., 2000 [15]	Dark chocolate	220	4770	21.7

Oral doses of (-)-epicatechin between 25 and 200 mg have been shown to be pharmacologically relevant. A 200 mg oral dose increased measures of plasma NO and decreased the vasoconstrictor endothelin-1 [52], while administration of an ~75 mg dose (1 mg/kg body weight) resulted in significant improvement in vascular function (FMD) [11]. A recent meta-analysis of clinical data reported that an intake of 25 mg (-)-epicatechin per day was associated with significant reductions in SBP and DBP [54].

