### 5.3.3 Conclusions

(-)-Epicatechin was well tolerated over the 50-200 mg dose range, with rapid absorption and first pass metabolism. Non-metabolized (-)-epicatechin represented <5% of the total (-)-epicatechin compounds by 30 minutes. (-)-Epicatechin and its metabolites were rapidly cleared from the body with a plasma elimination half-life of approximately 2.5 hrs for the 100 and 200 mg doses. Plasma concentration of (-)-epicatechin was generally proportional to the administered dose. The 3 dominant groups of metabolites in our study were glucuronidated, sulfated and methyl sulfated, consistent with a recently published evaluation of (-)-epicatechin pharmacokinetics and metabolism [47]. A novel finding in this study was that the  $AUC_{\text{Metabolite}}/AUC_{\text{epicatechin}}$  ratio increased with increasing doses suggesting dose dependency of (-)-epicatechin metabolism.

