## 8 ASSESSMENT OF EFFICACY

### 8.1 Laboratory Efficacy Parameters

- Peripheral Blood Tests

Peripheral venous blood will be collected at points specified in the study visit chart to evaluate:

- Creatine phosphokinase (CPK)

- Follistatin
  - mRNA and miRNA biomarker profiles
  - Pharmacokinetics: epicatechin metabolites [serum tested at trough, 2 hours (Tmax), 4 hours after dose at baseline, week 2, week 4 and week 8].
  - Blood lactate testing during exercise: Blood lactate levels will be collected at baseline and 2-minute intervals by finger-stick or ear-stick during 6-minute cycle testing.
- Muscle Biopsy (Biceps Brachii)

Open biopsies of the mid-biceps will be conducted at baseline and after 8 weeks of study medication dosing. The muscle biopsy samples will be collected by open biopsy or according to standard hospital procedures. The minimum amount of muscle tissue required is a small piece of muscle of at least 0.5 x 1.0 x 1.0 cm. If possible, the tissue collected will be of sufficient size to provide 4 (four) pieces of tissue (each 0.5x0.5x0.5cm). Muscle for histological evaluation will be sent fresh to hospital pathology. Muscle tissue for evaluation at outside labs will be immediately frozen in liquid nitrogen-cooled 2-methylbutane and stored at -80°C or -70°C till shipment. Biopsy at baseline will be collected from the lateral aspect of the midpoint of the biceps muscle without the use of depolarizing agents or Bovie catheterization prior to tissue extraction. Biopsy at 8 weeks will be collected from medial aspect of the midpoint of the biceps muscle of the same arm, and must be separated by a margin of at least 1cm to avoid scar tissue from the earlier biopsy.

Histology samples will be evaluated ([name] lab, UC Davis) to examine:

- Fiber size variation
- Tissue necrosis
- Degree of central nucleation
- Presence of basophilic/regenerating fibers
- Fiber type (myosin IHC stains)
- NADH-TR and succinic dehydrogenase (mitochondria)

Muscle biopsy samples will be examined by Western blot ([name] lab, UC San Diego) to evaluate:

Initial Phase (done immediately upon biopsy)

- Muscle regeneration: follistatin, MyoD, myogenin, dystrophin, sarcoglycans, dysferlin
- Oxidation/oxidative stress: SOD1, SOD2, catalase, GSK, nNOS, eNOS
- Mitochondrial function: ETC-I, ETC-V, mitofilin, porin
- Transcriptional regulation: PGC1-alpha
- Collagen deposition: Collagen I, collagen III, fibronectin

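### The PK dose-reduction trigger of 4 umol/ml is 839 times the highest peak in Table 2 and 70 times a whole 50 mg dose held in plasma, so it cannot fire as written

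*Combined protocol and SAP*

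**What the plan says.** Section 6.3.2 gives five grounds for reducing the dose. The first is "Peak (-)-epicatechin PK level >4umol/ml"; the others are headache, changes in safety laboratory values, abnormal coagulation and other Grade 4 events. Table 4 sets the consequence: the first reduction takes the participant from 100 to 50 mg/day, and the second stops study drug. Doses are not raised again.

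The protocol's own pharmacokinetic background is on a different scale. Section 3.1 states: "Total plasma concentrations of (-)-epicatechin plus its metabolites are found in the low-micromolar range". The relevant column of Table 2 is headed "Peak (-)-Epicatechin Species in Plasma (nM"), and its entries run from 630 to 4,770. The text below Figure 3 adds "Oral bioavailability (peak plasma concentration/mg ingested) for (-)-epicatechin in cocoa/chocolate is ~10-20 nM/mg ingested (Table 2").

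The name of the measured substance varies. Section 6.3.2 refers to (-)-epicatechin. Aim 3 (section 1.4) does the same: "Pharmacokinetic studies will include repeat assessments of trough, 2 hour-post (peak) and 4-hour post dose (-)-epicatechin levels". Section 8.1 instead has "Pharmacokinetics: epicatechin metabolites [serum tested at trough, 2 hours (Tmax), 4 hours after dose", and Table 2 reports species.

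**The concern.** A threshold in umol/ml is a thousand times one in umol/L. Read literally, the criterion asks for 4 mmol/L of a compound whose total level the protocol places in the low-micromolar range. If no participant on 50 mg twice daily can reach that level, the rule is void, although samples at the nominal peak are drawn at baseline and weeks 2, 4 and 8.

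What would be lost is specific. The other four criteria respond to symptoms, laboratory changes or adverse events. Only this one could identify a participant with unusually high exposure before an effect appears. Staff who noticed the problem might also apply a unit of their own choosing, so the rule in use would no longer be the written one.

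The analyte matters for a related reason. Parent drug is a small fraction of the total, so a corrected number may be reachable for total species and still out of reach for parent drug.

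**Working it through.** **Inputs from the protocol**

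- Threshold: 4 umol/ml (6.3.2) = 4 mmol/L = 4,000,000 nM.
- Dose: 50 mg twice daily, about 12 h apart (6.3.1).
- Molecular weight: 290.27 g/mol (7.2.1).
- Plasma volume: 3 L, from "Assuming ~3L plasma in a 75 kg man" (3.1).
- Peak per mg: 7.2 to 21.7 nM/mg across the rows of Table 2.
- Half-life: about 2.5 h (5.3.3).

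**The protocol's own figure.** Section 3.1 estimates that 1-2% of a dose is in plasma at the peak, counting parent and metabolites. One mg is 1,000,000 / 290.27 = 3,445 nmol. At 10 nM/mg, 3 L holds 30 nmol, and 30 / 3,445 = 0.87%. At 20 nM/mg it holds 60 nmol, which is 1.74%. These round to the stated 1-2%, so the background figures agree with one another in nM.

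**Threshold against Table 2**

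| Table 2 row | Peak (nM) | 4,000,000 / peak |
|---|---|---|
| 55 mg, cocoa drink (lowest) | 630 | 6,349 |
| 200 mg, pure compound | 3,570 | 1,120 |
| 220 mg, dark chocolate (highest) | 4,770 | 839 |

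**Threshold against the expected study peak.** 50 x 7.2 = 360 nM and 50 x 21.7 = 1,085 nM. The ratios are 4,000,000 / 360 = 11,111 and 4,000,000 / 1,085 = 3,687.

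**Mass balance.** This check needs no absorption model. 50 mg / 290.27 g/mol = 172.3 umol. Spread through 3,000 ml, that is 172.3 / 3,000 = 0.0574 umol/ml, and 4 / 0.0574 = 69.7. Holding the whole 100 mg daily dose in plasma still leaves a factor of 34.8. Reaching the threshold would need 4 mmol/L x 3 L x 290.27 g/mol = 3,483 mg in plasma at once.

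**Sensitivity**

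- Plasma volume of 2 to 4 L (assumed range): the 50 mg ratio runs from 46 to 93.
- Accumulation: 2^(-12/2.5) = 0.036 and 1 / (1 - 0.036) = 1.04, so the expected peak becomes 373 to 1,125 nM.
- Oral dose needed if peak rises linearly with dose: 4,000,000 / 21.7 = 184 g to 4,000,000 / 7.2 = 556 g. This is illustrative only.

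**If the unit were umol/L.** The threshold becomes 4,000 nM, between the two highest Table 2 peaks. Against the expected 50 mg peak of total species, 4,000 / 1,085 = 3.7 and 4,000 / 360 = 11.1. Under linearity this corresponds to a single dose of 184 to 556 mg.

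**If it were then applied to parent drug only.** Section 5.3.3 states: "Non-metabolized (-)-epicatechin represented <5% of the total (-)-epicatechin compounds by 30 minutes". That gives at most 0.05 x 1,085 = 54 nM, and 4,000 / 54.25 = 74. Even the corrected threshold would be effectively unreachable.

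**The case against.** The unit error itself is hard to dispute: no other section gives the threshold differently, and micromolar units elsewhere in the protocol are printed properly. The case on the other side concerns its weight and the remedy.

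- **Little protection is lost.** Four criteria remain. Section 9.5 allows withdrawal for SAEs, intolerable events and laboratory abnormalities, and a Medical Monitor reviews events. The protocol reports no adverse effects in nine volunteers given single doses of 50 to 200 mg, and an 85-fold margin to the rat NOAEL. The corrected threshold would seldom fire either. This stands as a limit on the consequences. It does not justify leaving an operative safety rule with a number that cannot be reached.
- **The analyte is clear enough in context.** Section 3.1 uses the parent name when counting parent and metabolites together, and 8.1 names metabolites, so total species is the natural reading. That is fair: the wording is ambiguous and does not prove that trigger and assay differ. The ambiguity still decides whether the corrected threshold can be reached.
- **Linear extrapolation is weak.** Section 5.3.2 reports that metabolite AUC per mg rises with dose, and the 21.7 nM/mg figure comes from a 220 mg dose. The row nearest the study dose gives 50 x 11.5 = 575 nM. This limits the extrapolated doses and makes the upper end of the expected peak uncertain. It does not affect the 839-fold or 70-fold ratios.
- **Assay turnaround is not stated.** A late result could leave even a corrected rule inactive, and a week 8 result comes too late to alter dosing. That is a separate question from the unit.

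**Conclusion.** The concern holds. At 50 mg twice daily the PK criterion cannot be met as written: it is 839 times the highest peak in Table 2, about 3,700 to 11,100 times the expected peak, and 70 times the level if the whole dose were in plasma. The first ratio is pure unit conversion. The second assumes that Table 2's per-mg exposures apply to these participants. The third rests only on the stated molecular weight and plasma volume, and no plausible plasma volume or accumulation closes the gap.

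The effect is confined to one of five dose-reduction criteria, and no efficacy or safety endpoint depends on it. It is nevertheless the trial's only exposure-based trigger and carries a mandatory dose change, so it must be corrected. That umol/L was intended is the most plausible explanation, but it remains an inference.

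**What to change.** In section 6.3.2, correct the unit, most plausibly to >4 umol/L, and state that the limit applies to total (-)-epicatechin species, parent plus metabolites, as in Table 2. Use the same analyte name in 6.3.2, Aim 3 and section 8.1.

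Before the text is finalised, the clinical team should confirm the value as well as the unit, knowing that 4 umol/L of total species would act only on outliers. If they want a trigger closer to the expected range, the number itself has to change.

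The cost is a wording change in three places and one clinical confirmation. The 2-hour samples are already scheduled, so no new sample, visit or procedure is needed.
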